A Randomized Controlled Trial of patients undergoing Percutaneous Coronary Intervention who receive Ticagrelor and Fentanyl

FACTPCI (Fentanyl and Crushed Ticagrelor PCI) trial

Protocol dated October 28, 2019

Principal Investigator: [name] MD

Sub-Investigators:

[name] MD, [name] MD, [name] MD and [name] MD.

The Guthrie Clinic
[name]
[name]

Background:

[figure not shown]
Ticagrelor is an orally administered P2Y12 receptor antagonist in patients undergoing percutaneous coronary intervention (PCI).¹ Ticagrelor inhibits platelet activation and aggregation. Fentanyl is routinely administered as conscious sedation during the PCI procedures. Recent studies have shown that Opioid analgesics delay P2Y12 receptor antagonist mediated platelet aggregation.² Delay in platelet aggregation could lead to increased adverse events including stent thrombosis, myocardial infarction and death. In a recent trial, impact of Fentanyl on Ticagrelor mediated platelet aggregation was evaluated.³ There was delayed platelet aggregation with increased adverse clinical events in patients receiving Fentanyl and Ticagrelor. This was felt to be related to decreased absorption of Ticagrelor leading to delayed platelet aggregation. However, a recent study showed that crushed Ticagrelor has more bioavailability and reaches peak earlier than oral Ticagrelor.^{4, 5} Based on these results, it could be hypothesized that crushed Ticagrelor might mitigate some of the ill effects of Fentanyl. Hence, we propose this trial to assess the impact of Fentanyl on platelet aggregation in patients receiving crushed Ticagrelor during PCI.

Objective:

The primary objective is to test the influence of Fentanyl on pharmacodynamics of crushed vs non-crushed ticagrelor in patients who are undergoing PCI.

Methods & design:

Single center, randomized clinical trial designed to assess the influence of Fentanyl on pharmacodynamics of crushed vs non- crushed ticagrelor in patients undergoing PCI at Robert Packer Hospital. The plan is to enroll 80 patients in this study. Forty patients each in the elective and non-elective PCI groups. Further In each group, patients will be randomized in a 1:1 ratio to either crushed or non-crushed Ticagrelor arms.

Inclusion criteria:

- Patients \geq 18 years of age
- Undergoing clinically indicated elective or non-elective PCI
- Able to swallow oral medications

Exclusion criteria:

- Contraindications to ticagrelor or fentanyl (or other opiates)
- Pregnancy
- Any use of P2Y₁₂ inhibitors within 14 days
- Known coagulation disorders
- Pre-procedural treatment with an anticoagulant (oral anticoagulant or low molecular weight heparin)
- Platelet count $< 100,000/\text{mm}^3$
- Impaired renal function (Estimated glomerular filtration $< 45 \text{ ml/min}/1.73 \text{ m}^2$)
- Impaired hepatic function (Based on medical history)
- Prior or planned transcatheter aortic valve replacement

Treatment protocol

- All patients will be medicated with at least Fentanyl 25 mcg Intravenously prior to start of the procedure. Additional sedation will be at the discretion of the treating physician.
- In the crushed Ticagrelor arm, subjects will receive 180 mg of crushed Ticagrelor, which will be crushed using EZY CRUSH pill crusher and mixed with 30 cc of drinking water, whereas patients in the other arm will receive an integral tablet of Ticagrelor loading dose (180 mg).
- Platelet function testing (PFT) in each patient will be performed (platelet vasodilator-stimulated phosphoprotein assay, multiple electrode aggregometry, Verify Now assay).
- The PFT will be performed at randomization, 30 mins, 2, 4, and 6-hour intervals from the time of Ticagrelor administration. Blood (2cc filled completely) will be collected in blue top tubes (coag sodium citrate 3.29). The platelets must not be disturbed by jarring after collection. The blood must not be shaken after collection, and it must be hand carried to the lab. At each sampling time point a second blue top tube will be collected for sampling assurance. The first sample at each time point will be processed. If a testing error occurs the second sample will be processed for data purposes.
- Patients will be treated according to current American Heart Association / American College of Cardiology guidelines.
- The choice of the access of the procedure (radial or femoral) and the type of implanted stent will be at the discretion of the operator.
- All patients will receive maintenance doses of ticagrelor (90 mg) twice daily post

PCI.

Risks:

It is expected that the risk of taking Ticagrelor crushed is the same as taking Ticagrelor not-crushed. The crushed tablet may enter the blood stream faster. There may be risks that are not known. The risks of Ticagrelor are provided in the package insert

https://www.accessdata.fda.gov/drugsatfda_docs/label/2016/022433s020lbl.pdf

Benefits:

The potential benefit to patients is that crushed Ticagrelor may have more bioavailability and reach peak earlier than non-crushed Ticagrelor. Crushed Ticagrelor may be useful to use following conscious sedation with Fentanyl, and may counter the delay in P2Y12 receptor antagonist mediated platelet aggregation that is associated with Fentanyl. Improved inhibition of platelet aggregation may lead to reduced adverse events including stent thrombosis, myocardial infarction and death.

For patients who are randomized to receive the non-crushed Ticagrelor, there is no anticipated benefit as this would be what is routinely done.

Study endpoints:

- The primary endpoint is the area under the PFT-time curve (AUC (0–6)) for the first 6 hours after the loading dose of Ticagrelor
- The secondary end points at discharge and 30 days are as follows -
 - Stent thrombosis
 - Recurrent myocardial infarction
 - All-cause mortality
 - Stroke
 - TIMI minor and major

Data Collection:

Information regarding patient characteristics will be obtained from the electronic medical record. Data will include: medical record number; age; sex; race; BMI; and medical history; date of PCI; radial or femoral access of the procedure; type of implanted stent; crushed or non-crushed ticagrelor; platelet function testing at baseline, 30 min, 2, 4, and 6, hours. Data will be collected at discharge and 30 days to include events of: stent thrombosis, recurrent myocardial infarction, all-cause mortality, stroke, or TIMI.

Statistics

- All continuous data will be expressed as mean \pm standard deviation and compared

- using a two-tailed Student's t-test when appropriate or the Mann-Whitney U test.
- Categorical variables will be expressed as a percentage and compared using chi-square or Fisher's exact test when appropriate.

Discussion:

This study is expected to provide crucial data on the influence of Fentanyl on crushed vs non-crushed Ticagrelor associated platelet function in patients undergoing PCI. The findings of this study would have a major impact on clinical practice as Fentanyl is currently used as sedation in more than 95% of patients undergoing PCI.

References:

Statistical Analysis Plan

Title: Fentanyl and Crushed Ticagrelor (FACT) PCI: A Randomized Control Trial of Patients Undergoing Percutaneous Coronary Intervention with Fentanyl and Crushed or Integral Ticagrelor and Comparison of Platelet Reactivity

Version 2.1

December 10, 2025

Table of Contents

Version History	3
Introduction	3
a. Background and Rationale	3
b. Study Objectives	3
Study Design	3
a. Study Overview	3
Research location	3
Design and Hypotheses	4
Summary of Endpoints:	4
b. Study Groups	4
Recruitment and Consent	4
Randomization and Allocation Concealment:	4
Blinding:	5
Inclusion criteria:	5
Exclusion criteria:	5
c. Intervention	5
d. Sample Size	6
Outcomes	6
a. Primary Outcomes	6
b. Secondary Outcomes	7
c. Other Prespecified Outcomes	7
Statistical Analysis	7
a. General Considerations	7
b. Baseline Data	8
c. Primary Outcomes	8
d. Secondary Outcomes	9
e. Software	9
References:	9

Version History

Version	Date	Author	Changes
1.0	October 15, 2025	[name]	Initial version
2.0	October 31, 2025	[name]	Updated to reflect early stopping decision.
2.1	December 10, 2025	[name]	Clarified language in data analysis section, updated software.

Introduction

a. Background and Rationale

Ticagrelor is an orally administered P2Y12 receptor antagonist in patients undergoing percutaneous coronary intervention (PCI)¹. Ticagrelor inhibits platelet activation and aggregation. Fentanyl is routinely administered as conscious sedation during the PCI procedures. Recent studies have shown that Opioid analgesics delay P2Y12 receptor antagonist mediated platelet aggregation². Delay in platelet aggregation could lead to increased adverse events including stent thrombosis, myocardial infarction and death. In a recent trial, the impact of Fentanyl on Ticagrelor mediated platelet aggregation was evaluated³. There was delayed platelet aggregation with increased adverse clinical events in patients receiving Fentanyl and Ticagrelor. This was thought to be related to decreased absorption of Ticagrelor leading to delayed platelet aggregation. However, a recent study showed that crushed Ticagrelor has more bioavailability and reaches peak earlier than oral Ticagrelor^{4,5}. Based on these results, it could be hypothesized that crushed Ticagrelor might mitigate some of the ill effects of Fentanyl. Hence, we propose this trial to assess the impact of Fentanyl on platelet aggregation in patients receiving crushed Ticagrelor during PCI.

b. Study Objectives

The primary objective is to test the influence of Fentanyl on pharmacodynamics of crushed vs non-crushed (integral) ticagrelor in patients who are undergoing PCI.

Study Design

a. Study Overview

Research location

The study is conducted at The Guthrie Clinic, Robert Packer Hospital, [name].

Design and Hypotheses

The study is a single center, randomized clinical trial designed to assess the influence of Fentanyl on pharmacodynamics of crushed vs non- crushed ticagrelor in patients undergoing PCI at Robert Packer Hospital.

Hypothesis: In patients undergoing PCI who receive fentanyl for conscious sedation, *crushed* ticagrelor produces faster and greater inhibition of platelet function over the first 6 hours after a loading dose than *non-crushed* ticagrelor, as measured by a smaller AUC_{0-6} of the platelet-function test.

- **H_0 (null):** There is no difference in the AUC_{0-6} of platelet function between fentanyl-sedated PCI patients receiving crushed ticagrelor and those receiving non-crushed ticagrelor.
- **H_1 (alternative):** The AUC_{0-6} of platelet function is lower (indicating greater platelet inhibition) in fentanyl-sedated PCI patients receiving crushed ticagrelor compared with non-crushed ticagrelor.

Summary of Endpoints:

- The primary endpoint is the area under the Platelet Function Testing (PFT)-time curve (AUC_{0-6}) for the first 6 hours after the loading dose of Ticagrelor.
- The secondary end points at discharge and 30 days:
 - Stent thrombosis
 - Recurrent myocardial infarction
 - All-cause mortality
 - Stroke
 - TIMI minor and major

b. Study Groups

Recruitment and Consent

Recruitment: Participants will be recruited from Robert Packer Hospital patients who are undergoing elective or non-elective PCI. Participants will be screened for eligibility and those who meet the inclusion/exclusion criteria will be invited to take part.

Consent: Written consent will be required for all study participants prior to participation and will be obtained by the principal investigator (PI) or a sub-investigator. After fulfilling the inclusion and exclusion criteria, consent will be obtained.

Randomization and Allocation Concealment

Randomization: Subjects are randomized by simple randomization which remained concealed from the researchers until the end of enrollment. Randomization was done by a random number

generated computer program using Research Randomizer (Version 4.0) by someone not involved in the research. The randomization schedule was placed in sealed envelopes to be concealed from the researcher until time of consent.

Urbaniak, G. C., & Plous, S. (2013). Research Randomizer (Version 4.0) [Computer program]. <http://www.randomizer.org/>

Blinding

The study is not blinded.

Inclusion criteria

- Patients \geq 18 years of age
- Undergoing clinically indicated elective or non-elective PCI
- Able to swallow oral medications

Exclusion criteria:

- Contraindications to ticagrelor or fentanyl (or other opiates)
- Pregnancy
- Any use of P2Y₁₂ inhibitors within 14 days
- Known coagulation disorders
- Pre-procedural treatment with an anticoagulant (oral anticoagulant or low molecular weight heparin)
- Platelet count $< 100,000/\text{mm}^3$
- Impaired renal function (Estimated glomerular filtration $< 45 \text{ ml/min}/1.73 \text{ m}^2$)
- Impaired hepatic function (Based on medical history)
- Prior or planned transcatheter aortic valve replacement

c. Intervention

Treatment protocol

- All patients will be medicated with at least Fentanyl 25 mcg intravenously prior to start of the procedure. Additional sedation will be at the discretion of the treating physician.
- In the crushed Ticagrelor arm, subjects will receive 180 mg of crushed Ticagrelor, which will be crushed using EZY CRUSH pill crusher and mixed with 30 cc of drinking water, whereas patients in the other arm will receive an integral tablet of Ticagrelor loading dose (180 mg).
- Platelet function testing (PFT) in each patient will be performed (platelet vasodilator-stimulated phosphoprotein assay, multiple electrode aggregometry, Verify Now assay).
- The PFT will be performed at randomization, 30 mins, 2, 4, and 6-hour intervals from the time of Ticagrelor administration. Blood (2cc filled completely) will be collected in blue top tubes (coag sodium citrate 3.29). The platelets must not be disturbed by jarring after collection. The blood must not be shaken after collection, and it must be hand carried to the lab. At each sampling time point, a second blue top tube will be collected for sampling

assurance. The first sample at each time point will be processed. If a testing error occurs, the second sample will be processed for data purposes.

- Patients will be treated according to current American Heart Association / American College of Cardiology guidelines.
- The choice of the access of the procedure (radial or femoral) and the type of implanted stent will be at the discretion of the operator.
- All patients will receive maintenance doses of ticagrelor (90 mg) twice daily post PCI.

d. Sample Size

This is an exploratory study; therefore, no formal sample size calculation was conducted. The planned sample size is based on feasibility considerations and is considered sufficient to generate preliminary estimates and assess study procedures.

The study plans to enroll 80 participants, 40 participants who had elective PCI and 40 participants who had non-elective (emergent) PCI.

Update to Sample Size 10/31/2025: The study was terminated prematurely on January 27, 2025 due to a poor accrual rate. Challenges were encountered in recruitment in the post-COVID-19 era in the rural community hospital along with increased use of Cangrelor in subjects with ACS. The increased utilization of other therapeutic agents, such as generic prasugrel further reduced the recruitment and relevance of this study.

There were a total of 45 participants randomized at the time the study closed to accrual. Of the 45, seven participants withdrew, leaving a total of 38 participants for analysis. Due to the small sample size, the data from elective (scheduled) and non-elective (emergent) PCI will be combined for analysis to compare crushed versus non-crushed Ticagrelor.

Outcomes

a. Primary Outcomes

The primary outcome is the area under the PFT-time curve (AUC₀₋₆) for the first 6 hours after the loading dose of Ticagrelor.

Platelet Function Testing will be collected at 5 time-points after Ticagrelor administration.

- Baseline (time 0) – immediately prior to ticagrelor loading dose
- 0.5 hours after dose
- 2 hours after dose
- 4 hours after dose
- 6 hours after dose

The actual clock time for each draw will be collected.

The Platelet Function Testing assay will be *VerifyNow Platelet Reactivity Assay* which is used institutionally. Results are reported in platelet reactive units (PRUs). Based on previous studies,

208 will be used as an estimated cutoff to distinguish therapeutic and subtherapeutic platelet inhibition, with PRUs equal to or less than 208 being considered therapeutic⁶.

b. Secondary Outcomes

The secondary outcomes are:

- Stent thrombosis at discharge
- Stent thrombosis at 30 days
- Recurrent myocardial infarction at discharge
- Recurrent myocardial infarction at 30 days
- All-cause mortality at discharge
- All-cause mortality at 30 days
- Stroke at discharge
- Stroke at 30 days
- TIMI bleeding (minor and major, per TIMI criteria) at discharge
- TIMI bleeding (minor and major, per TIMI criteria) at 30 days

Time-window rules (apply to all endpoints):

“At discharge” = events occurring during the index hospitalization from time of ticagrelor loading dose until the formal hospital discharge time (documented in chart).

“At 30 days” = events occurring from time of ticagrelor loading dose up to 30 days (day 30 inclusive). Events that already occurred during index hospitalization are counted in the “at discharge” endpoint and also contribute to cumulative 30-day counts. The exact event date/time must be recorded.

Events will be identified through review of the electronic medical record, discharge summaries, procedure reports, and 30-day follow-up documentation or contact.

For each outcome, the presence or absence of the event will be recorded for each participant at both time points.

c. Other Prespecified Outcomes

Other prespecified outcomes include:

- Hospital Length of Stay (Hours)
- Hospital Readmission within 30 days

Statistical Analysis

a. General Considerations

Due to the premature termination and small sample size, the data from elective (scheduled) and non-elective (emergent) PCI will be combined for analysis to compare crushed versus non-

crushed Ticagrelor. The analysis of the primary outcome will be per protocol, as it is a sum across five timepoints and any patient with incomplete data would necessarily have a lower score. The remaining tests will be performed on the intention-to-treat sample.

We will report absolute counts and their respective percentages for categorical variables, means and standard deviations for non-skewed numeric variables, or medians and interquartile ranges for numeric variables exhibiting notable skew (assessed graphically). Differences between treatments will be assessed using the Fisher exact test for categorical variables, t-tests for numeric variables exhibiting normality, and Mann-Whitney tests for skewed numeric variables.

The statistical significance of the results will be determined using at a two-sided p-value of less than 0.05. Missing data will be handled with listwise deletion on a test-by-test basis.

b. Baseline Data

Descriptive statistics of the study population will include:

- Demographics (age, gender, race)
- Prior or current imaging studies (to evaluate underlying propensity to ischemic pathophysiology)
- Presence of MI on admission (based on clinical presentation, electrocardiogram (EKG) changes, and/or elevated troponins)
- Cardiovascular risk factors and comorbidities
 - Smoking
 - Type 2 diabetes mellitus
 - Hypertension
 - Hyperlipidemia
 - Prior Coronary Artery Disease
 - Renal Insufficiency
 - Gastroesophageal Reflux Disease
 - Obstructive Sleep Apnea, and
 - Body Mass Index (BMI).

Standard definitions were used to classify patients as having or not having these comorbidities.

c. Primary Outcomes

PFT will be used to quantify the antiplatelet effect of a ticagrelor loading dose over the first 6 hours after administration. The primary outcome is the area under the platelet-function vs. time curve from 0 to 6 hours after the loading dose (AUC_{0-6}). AUC_{0-6} captures both the magnitude and the time course of platelet inhibition produced by ticagrelor.

AUC_{0-6} will be calculated using the linear trapezoidal rule with measured platelet function values at the actual elapsed times. If actual draw times deviate slightly from planned times, we use the actual elapsed hours.

The trapezoidal rule formula between two consecutive timepoints (t_i, t_{i+1}) with values y_i and y_{i+1} is:

$$\text{Area}_i = ((y_i + y_{i+1}) / 2) \times (t_{i+1} - t_i)$$

Total AUC = $\sum \text{Area}_i$ across intervals from 0 to 6 hours.

d. Secondary Outcomes

For each categorical secondary outcome, the count and percentage of patients experiencing the event in each group will be calculated at both discharge and 30 days. Between-group comparisons of event rates will be performed using Fisher's exact test (if expected cell counts <5). Length of stay will be summarized with medians and IQRs, and the p-value from a Mann-Whitney test will be reported.

e. Software

Data will be analyzed with R version 4.4.1, R Core Team, Vienna, Austria

References:

3. McEvoy et al. Effect of Intravenous Fentanyl on Ticagrelor Absorption and Platelet Inhibition Among Patients Undergoing Percutaneous Coronary Intervention: The PACIFY Randomized Clinical Trial. *Circulation AHA.* 2017;CIRCULATIONAHA.117.031678

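### The SAP pools elective and non-elective PCI, which the protocol enrols and randomises as two groups, and plans no result, count or adjustment by PCI type

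*SAP*

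**What the plan says.** **Protocol, Methods & design.** The target is 80 ("The plan is to enroll 80 patients in this study"), built from two groups: "Forty patients each in the elective and non-elective PCI groups". Within each group, "patients will be randomized in a 1:1 ratio to either crushed or non-crushed Ticagrelor arms". The Statistics section lists only general two-sample and categorical tests and specifies nothing by PCI type.

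**SAP, Design and Hypotheses.** The null and alternative concern fentanyl-sedated PCI patients as a whole.

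**SAP, Randomization and Allocation Concealment.** "Subjects are randomized by simple randomization which remained concealed from the researchers until the end of enrollment". PCI type is not mentioned there.

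**SAP, d. Sample Size.** "This is an exploratory study; therefore, no formal sample size calculation was conducted". The 40 + 40 plan is repeated. The update dated 31 October 2025 reports termination on 27 January 2025 for poor accrual. "There were a total of 45 participants randomized at the time the study closed to accrual"; seven withdrew, leaving 38. It then says: "Due to the small sample size, the data from elective (scheduled) and non-elective (emergent) PCI will be combined for analysis". Statistical Analysis, a. General Considerations, repeats the rule. The Version History describes version 2.0 as "Updated to reflect early stopping decision".

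**SAP, Statistical Analysis, a to d.** Arms are compared by Fisher, t or Mann-Whitney tests. There is no PCI-type term, by-type estimate or interaction. PCI type is absent from the baseline list, where MI on admission is the nearest item.

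**The concern.** PCI type is a design factor in this trial: the protocol used it to structure both enrolment and randomisation. Small numbers are a good reason to make the pooled comparison the headline. They are a weaker reason to report nothing by type, especially in a study the SAP calls exploratory and intends to yield preliminary estimates.

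Three things are at stake.

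- **Interpretation.** The pooled difference is an average over an elective/non-elective mix that the SAP does not state. If crushing acts differently in the two types, that average may describe neither, and no planned output would reveal it.
- **Balance.** The protocol places randomisation within each group, whereas the SAP describes simple randomisation. Simple randomisation does not ensure that PCI type is balanced between arms, and the planned tests do not adjust for it.
- **Transparency.** Pooling is recorded in an update dated after an unblinded trial had closed. Showing the components lets a reader judge the choice.

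**Working it through.** **The plan's own figures.** 40 + 40 = 80 planned. 45 − 7 = 38 for analysis. Both reproduce. There is no power calculation to reproduce. From 27 January to 31 October 2025 is 277 days.

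**Assumptions not in the documents.** All 38 curves are complete, and arms are equal (19 v 19). PCI types are split evenly (9 v 10 in each) unless stated. Effects are in units of the within-type SD of AUC0-6. Tests are two-sided at 0.05, as in the SAP. The true split is not given. Because the primary analysis is per protocol and excludes incomplete curves, 38 is a ceiling.

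**Dilution.** If the effect is d in one type with share s, and zero in the other, the pooled effect is s × d. With n per arm, power comes from the noncentral t distribution with noncentrality effect/√(1/n₁ + 1/n₂).

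At s = 0.5 and d = 1.0, the pooled effect is 0.5 SD. With 19 v 19, power is 32%. An effect in one type only also adds spread in the crushed arm. Averaged over arms, the variance becomes 1 + s(1 − s)d²/2 = 1 + 0.25/2 = 1.125. The standardised effect is then 0.5/√1.125 = 0.47, and power is 29%.

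Allowing for that spread, with d = 1.0:

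| Share of the type with the effect | Pooled effect | Pooled power | Power within that type | Interaction power |
|---|---|---|---|---|
| 25% | 0.25 SD | 11% | 27% | 25% |
| 50% | 0.50 SD | 29% | 54% | 32% |
| 75% | 0.75 SD | 58% | 73% | 25% |

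With d = 1.5, pooled power is 17%, 51% and 87% at the same shares.

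**Same effect in both types.** At d = 1.0 in both, pooled power (19 v 19) is 85%, against 54% in either type alone (9 v 10).

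**Precision.** The 95% half-width is t × √(sum of 1/n over the cells compared).

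- Pooled, 19 v 19: 2.028 × √(2/19) = 0.66 SD.
- Within a type, 9 v 10: 2.110 × √(1/9 + 1/10) = 0.97 SD.
- Interaction, even split, 34 df: 2.032 × √(2/9 + 2/10) = 1.32 SD.
- If one type supplied only 10 patients (5 v 5): 2.306 × √(2/5) = 1.46 SD. The interaction would then be 2.032 × √(2/5 + 2/14) = 1.50 SD.

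**Chance imbalance.** With 19 per arm and half of each type, the standard deviation of the between-arm difference in the proportion non-elective is √(2 × 0.5 × 0.5/19) = 0.16. A gap of 16 percentage points is therefore an ordinary outcome if type is not balanced by design. The unadjusted comparison would shift by that gap times the mean AUC0-6 difference between types, which the documents do not give.

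**The case against.** The strongest reply is that pooling answers the question the trial asks. The objective and hypotheses cover PCI patients overall, and neither document hypothesises that crushing works differently by PCI type. With 38 patients, pooling is also the more powerful choice if the effect is common to both types (85% against 54%). By-type tests would need a multiplicity allowance: a Bonferroni split over the two types lowers 54% to 41%. Intervals of ±0.97 SD or more could expose only a very large difference. The SAP already discloses the pooling with its reason, closure date and update date. All of this stands, and it is why the pooled comparison should remain the headline.

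It does not explain why the factor used to structure randomisation should be missing from the participant counts, the baseline list and the model. Nor does low power rule out a descriptive estimate with an interval that shows its own imprecision.

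A reader might infer more than the documents support:

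- **That a prespecified by-type test was dropped.** The protocol's Statistics section never promised one.
- **That two full groups of 40 are merged.** Those groups were not filled; 38 patients in total are pooled.
- **That an effect in one type would vanish.** It is diluted by that type's share, and a large effect in the larger type could still reach significance. What is always lost is its attribution to a type.
- **That the SAP reports a loss of non-elective patients.** It names cangrelor use in ACS as one of several accrual problems and gives no figures by PCI type.
- **That pooling was chosen after looking at results.** The update is late and the trial unblinded, but nothing shows that anyone had compared the arms.

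**Conclusion.** The concern holds as a reporting and adjustment gap; the pooled headline itself is sound. As written, the SAP cannot show whether the crushed-integral difference varies between elective and non-elective PCI, cannot show what mix the pooled estimate averages over, and does not guard against imbalance of PCI type between arms.

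The size depends on the unstated split. For a 1.0 SD effect in one type only, the pooled effect is 0.25 to 0.75 SD for shares of 25% to 75%, with pooled power of 11% to 58%. An even split gives 0.5 SD and about 29-32%. The effect sizes, the even split and complete curves are my assumptions. That no by-type output or adjustment is planned can be read directly from the SAP.

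The change is worth making because it is cheap and follows the protocol's own structure. It would not make 38 patients sufficient to establish a subgroup effect.

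**What to change.** Keep the pooled crushed-versus-integral comparison as primary. In SAP Statistical Analysis, c. Primary Outcomes, add:

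1. The numbers randomised, withdrawn and analysed, by PCI type and arm.
2. The crushed-minus-integral AUC0-6 difference with 95% CI within each PCI type, and the treatment-by-type interaction with 95% CI. Label these descriptive, with no significance claim by type.
3. PCI type as a term in the pooled comparison, for example a linear model of AUC0-6 on arm and PCI type. This handles imbalance between arms but still gives a single average effect, so it complements item 2 and does not replace it.

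The SAP should also say whether randomisation was carried out separately within each PCI group, since its description and the protocol's differ.

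The cost is one table, one model term and a few sentences, with no new data beyond each patient's PCI type. The downside is wide intervals: about ±0.97 SD within a type and ±1.32 SD for the interaction under an even split, and wider if the split is uneven or curves are incomplete. The text should say plainly that these cannot support subgroup claims.

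### The primary AUC(0-6) is confined to an undefined per-protocol set that appears to drop anyone with a missing draw, for a reason that is wrong for interior draws and does not require exclusion

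*SAP*

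**What the plan says.** All of the following is in the SAP unless stated otherwise.

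- Statistical Analysis, a. General Considerations: "The analysis of the primary outcome will be per protocol", with the reason "as it is a sum across five timepoints and any patient with incomplete data would necessarily have a lower score". For everything else, "The remaining tests will be performed on the intention-to-treat sample". On missing values in general, "Missing data will be handled with listwise deletion on a test-by-test basis".
- Statistical Analysis, c. Primary Outcomes: the AUC "will be calculated using the linear trapezoidal rule with measured platelet function values at the actual elapsed times". The area formula is introduced with "The trapezoidal rule formula between two consecutive timepoints" and summed over the intervals from 0 to 6 hours. Small deviations in draw time are covered. A draw that was not taken is not.
- Outcomes, a. Primary Outcomes: five draws, at 0, 0.5, 2, 4 and 6 h. Study Design, c. Intervention: a second tube is used if a test fails.
- Study Design, d. Sample Size: "Of the 45, seven participants withdrew, leaving a total of 38 participants for analysis". The study is described as exploratory, with no sample-size calculation.

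Neither document says what places a participant in the per-protocol set. No dosing, fentanyl, timing or minimum-draw criterion is given, and the protocol's Statistics section names no such set.

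**The concern.** The reason given is about arithmetic, not adherence. Together with the listwise rule, it suggests that the per-protocol set means participants with all five readings. That is an inference, because the SAP does not say so.

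If the inference is right, three things follow. A participant with four valid readings contributes nothing to the primary analysis. Entry to the primary comparison depends on something that happens after randomisation, in a trial the SAP describes as unblinded. And the reader cannot judge the effect, because the SAP plans neither an AUC analysis of all available data nor a report of missing draws by arm. At stake are the primary estimate and its standard error. No powered test is affected, since none was planned.

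**Working it through.** **The plan's own figure.** 45 randomised − 7 withdrawn = 38. This reproduces. There is no power calculation to check.

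**Does a missing draw necessarily lower the AUC?** The formula is the SAP's: area = ((y₁ + y₂)/2) × (t₂ − t₁), summed. At 0, 0.5, 2, 4 and 6 h it gives the readings weights of 0.25, 1, 1.75, 2 and 1 (sum 6). The documents contain no PRU data, so the profiles are assumed. For 230/210/120/60/40 PRU:

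0.25×230 + 1×210 + 1.75×120 + 2×60 + 1×40 = 57.5 + 210 + 210 + 120 + 40 = 637.5 PRU·h.

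If an interior draw is missing and the same trapezoid spans the gap, the AUC changes by (gap width / 2) × (chord value − missing reading). With 2 h missing, the chord from 210 at 0.5 h to 60 at 4 h is 145.7 at 2 h, so the change is (3.5/2) × (145.7 − 120) = +45.

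| Missing draw | Gap bridged, or curve cut short | Intervals touching the gap left out |
|---|---|---|
| 0 h | 527.5 | 527.5 |
| 0.5 h | 630.0 | 280.0 |
| 2 h | 682.5 | 210.0 |
| 4 h | 677.5 | 357.5 |
| 6 h | 537.5 | 537.5 |

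Change on bridging for other assumed profiles (0.5, 2, 4 h missing in turn):
- fast, 230/150/60/40/40 (full AUC 432.5): +37.5, +75, +20
- slow, 230/225/190/110/50 (885.0): −5, −25, +20
- flat, 200 throughout (1200): 0, 0, 0

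So a bridged interior gap can raise, lower or leave the AUC unchanged. The AUC must fall only if an end draw is lost without a rule, or if intervals next to the gap are omitted. The SAP does not say which treatment it has in mind.

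**How much could be lost?** The missing rate p per draw is assumed. With independent missingness the complete fraction is (1 − p)⁵, the SE factor is 1/√fraction, and the valid readings discarded are 38 × 5 × [(1 − p) − (1 − p)⁵]. The clustered columns assume a beta-binomial model with within-participant correlation 0.3.

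| p | Complete of 38, independent | SE rise | Readings discarded | Complete of 38, clustered | SE rise | Readings discarded |
|---|---|---|---|---|---|---|
| 3% | 0.859 × 38 = 32.6 | 8% | 21 | 35 | 5% | 11 |
| 5% | 0.774 × 38 = 29.4 | 14% | 33 | 33 | 8% | 18 |
| 10% | 0.590 × 38 = 22.4 | 30% | 59 | 28 | 17% | 32 |

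**Could the estimate shift?** This uses an assumed model: mean PRU 230/190/90/50/40 crushed and 230/212/140/75/50 non-crushed, SDs 45/60/70/45/30, AR(1) correlation 0.6, values held within 1 to 400. The full-data difference is about −159 PRU·h, with SE about 77 at 19 per arm. Suppose slow non-crushed responders (2 h PRU above 150) miss a late draw 10%, 15% or 25% of the time, against 5% for everyone else. The complete-curve effect then shrinks by about 3%, 6% or 13%. If fast non-crushed responders (2 h PRU 100 or below) do so instead, it grows by about 2.5%, 5% or 10%. The largest shift, about 20 PRU·h, is 20/77 ≈ 0.27 SE.

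**The case against.** The SAP has a fair defence. It does contain a general missing-data rule, so a partial curve is not left entirely without one. What it lacks is a definition of the set and an AUC-specific rule. Its worry is also sound for the end draws: without 0 h or 6 h, the AUC over 0 to 6 h cannot be computed from measured values, truncation lowers it, and the SAP's hypothesis counts lower as greater inhibition. That is a true missing-data problem and not only a matter of scoring. The second tube already deals with failed tests, which leaves mainly missed draws. Every magnitude above is assumed, independence gives larger losses than clustering, and the illustrated bias is small beside the sampling error of an exploratory study. All of this stands and limits the point.

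Three stronger readings may tempt a reader, and the documents support none of them:

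- *The rule cost seven participants.* The SAP attributes the fall from 45 to 38 to withdrawal and gives neither reasons nor timing. With both analysis sets undefined, per protocol could even mean those 38 and intention-to-treat the 45.
- *The rule favours crushed ticagrelor.* The shift can go either way, depending on who misses draws.
- *The set was chosen after seeing results.* Version 1.0 of the SAP is dated October 15, 2025, and "The study was terminated prematurely on January 27, 2025 due to a poor accrual rate". The order of dates does not show that PRU by arm had been examined.

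**Conclusion.** The concern holds in a limited form and should be fixed. The primary analysis set is undefined. Its apparent meaning, complete five-draw curves, would discard usable readings and condition the comparison on a post-randomisation event. The stated reason is incorrect for a bridged interior gap. It is correct for a lost end draw, but that does not require exclusion either.

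Confidence is high on the missing definition and the faulty reason, and low on the practical effect. The size depends on the number of incomplete curves, which the documents do not give and which may be zero. On the assumed rates, between 22 and 35 of 38 curves would be complete and the SE would rise by 5% to 30%.

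**What to change.** 1. Delete the lower-score rationale and the per-protocol restriction, and exempt the primary AUC from listwise deletion.
2. Analyse participants with usable PRU data by allocated arm. State whether any of the seven withdrawn participants contribute readings.
3. Bridge a missing interior draw with the same trapezoid at actual elapsed times. For a missing 0 h or 6 h draw, prespecify a model-based method that uses all available draws: either multiple imputation or a repeated-measures model giving the AUC contrast. Say how this works if the AUC is skewed and the Mann-Whitney test applies, since imputation alone does not settle that.
4. Keep the complete-curve AUC as a sensitivity analysis.
5. Report missing draws by arm and time point.
6. Because SAP version 1.0 post-dates termination, record the date of the change and whether PRU by arm had been seen. If it had, label the new analysis post hoc and show it beside the analysis now planned.

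The cost is SAP wording, one table and a short addition to the R code, with no new data. The price in assumptions is missing at random for end draws and a straight line across interior gaps. The straight line is not neutral (+45 on 637.5, or 7%, for the 2 h draw above), which is one reason to keep item 4. If every curve is complete and no withdrawn participant is added, the result is unchanged.
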